2.2.3 Dose-determining Set

The dose-determining set (DDS) consists of all patients from the safety set in the phase Ib dose escalation part who either meet the following minimum exposure criterion and have sufficient safety evaluations, or have experienced a DLT during the first two cycles.

A patient is considered to have met the minimum exposure criterion if he/she received two doses of MCS110 and PDR001 during the first two cycles.

Patients who do not experience a DLT during the first two cycles are considered to have sufficient safety evaluations if they have been observed for ≥ 42 days following the first dose, and are considered by both the Sponsor and Investigators to have enough safety data to conclude that a DLT did not occur.

Patients who do not meet these minimum safety evaluation requirements nor experience a DLT will be regarded as ineligible for the DDS and an additional patient may be recruited (see [\[CMCS110Z2102-CSP-Section 7.1.3.1\]](#)).

2.2.4 Pharmacokinetic Analysis Set

The pharmacokinetic analysis set (PAS) includes all patients who provide an evaluable PK profile. A profile is considered evaluable if all of the following conditions are satisfied:

- Patient receives one of the planned treatments
- Patient provides at least one primary PK parameter

Patients will be classified according to planned treatment group.

The PAS will be used for summaries of PK concentration data, PK parameters [REDACTED]

2.2.5 Withdrawal of Informed Consent

Any data collected in the clinical database before informed consent is obtained and after a withdraws informed consent from all further participation in the trial, will not be included in the analysis. The date on which a patient withdraws full consent is recorded in the eCRF.

2.2.6 Subgroup of interest

Not applicable.

2.3 Patient disposition, demographics and other baseline characteristics

Unless noted otherwise, summaries and listings described in this section will be based on the FAS.

2.3.1 Patient disposition

The FAS will be used for the patient disposition summary tables and listings. The following will be tabulated:

- Number (%) of patients who are still on-treatment (based on non-completion of the 'End of Treatment' page),
- Number (%) of patients who discontinued treatment (based on completion of the 'End of Treatment' page with discontinuation date entered),
- Primary reasons for study treatment discontinuation (based on discontinuation reason entered in the 'End of Treatment' page),

- Number (%) of patients who discontinued from post-treatment follow-up (based on completion of the 'End of Post Treatment Phase Disposition' page with discontinuation date entered),
- Primary reasons for post-treatment follow-up discontinuation (based on discontinuation reason entered in the 'End of Post Treatment Phase Disposition' page).

Protocol Deviation

Major protocol deviations leading to exclusion from analysis sets will be tabulated separately by treatment group for phase Ib and by patient group for phase II part. All protocol deviations will be listed. The full list of protocol deviations are documented in the Study Specification Document (SSD). Protocol deviations leading to exclusion from analysis sets and associated severity codes are specified in [Section 5.3](#).

2.3.2 Demographics

Demographic data including age, sex, predominant race, ethnicity, baseline weight and WHO/ECOG performance status will be listed and summarized.

In addition, child bearing potential, pregnancy test results will be listed, and age (18-< 65, 65-< 85, ≥ 85 years) categories summarized.

2.3.3 Other baseline characteristics

Medical history

Medical history and current (ongoing) medical conditions, including cancer-related conditions and symptoms, will be listed. Medical history and current medical conditions are coded using the latest Medical Dictionary for Regulatory Activities (MedDRA v23.0) terminology available at the time of reporting.

Prior anti-neoplastic therapies

Prior anti-neoplastic therapies will be listed for medication, radiotherapy and surgery.

The number (%) of patients who received any prior anti-neoplastic medication, radiotherapy or surgery will be summarized, separately.

The summary of prior anti-neoplastic medications will include the total number of regimens (note: there can be more than one medication per regimen), setting at last medication, and time (in days) from start of last medication to progression.

The last medication is defined based on the last end date of all prior regimen components. Prior antineoplastic medications will also be summarized by Anatomical Therapeutic Chemical (ATC) class, and preferred term.

The summary of prior anti-neoplastic radiotherapy will include the radiotherapy locations, (including all locations recorded for each patient) and setting at last radiotherapy.

The summary of prior anti-neoplastic surgery will include the time (in months) between the last surgery (non-biopsy procedure) to start of study treatment, procedure at last surgery (non-biopsy procedure) and residual disease at last surgery.

Consider specific imputation rules for partial dates in [Section 5.1.4](#).

Diagnosis and extent of cancer

The summary and listing of diagnosis and extent of cancer (disease history) will include primary site of cancer, histological grade, stage at initial diagnosis, time (in months) from initial diagnosis of primary site to start of study treatment, time (in months) since most recent recurrence/relapse or progression to start of study treatment, time (in months) from initial diagnosis of primary site to first recurrence/relapse or progression, current stage of cancer, current extent of disease (metastatic sites).

2.4 Treatments (study treatment, rescue medication, concomitant therapies, compliance)

The Safety Set will be used for all medication data summaries and listings.

2.4.1 Study treatment/compliance

Study treatment

MCS110 in combination with PDR001 (Q3W):

- Last date of *exposure* to study drug (MCS110) = last date of administration of MCS110 + 20 days
- Last date of *exposure* to study drug (PDR001) = last date of administration of PDR001 + 20 days
- Last date of *exposure* to study treatment (MCS110 + PDR001) = max (last date of MCS110 administration, last date of PDR001 administration) + 20 days = Date of last administration of study treatment + 20 days

Planned treatment: Planned treatment is the treatment to which a patient is assigned during enrollment.

Received treatment: Please refer to [Section 2.2.2](#).

Planned dose: Planned dose is the dose level(s) of study drug(s) corresponding to the planned treatment.

Prescribed dose: Prescribed dose is the dose level(s) of study drug(s) prescribed by doctor before study treatment is administered at beginning of each cycle.

Dose administered (mg/kg) for MCS110 = Dose prescribed (mg/kg) * Total volume administered (mL)/Total volume planned to be administered (mL);

Dose administered (mg) for PDR001 = Dose prescribed (mg) * Total volume administered (mL)/Total volume planned to be administered (mL);

Definitions of duration of exposure, cumulative dose, actual dose intensity (DI), planned dose intensity (PDI), relative dose intensity (RDI), as well as intermediate calculations, are as follows:

- **Duration of exposure (days) to study drug:** last date of *exposure* to study drug – first date of study drug + 1 (periods of interruption are not excluded);

- **Duration of exposure (days) to study treatment:** last date of *exposure* to study treatment – first date of study treatment + 1 (periods of interruption are not excluded);
- **Duration of exposure (weeks)** = Duration of exposure (days)/7;
- **Cumulative dose:** sum of all dose administered (mg/kg) to a patient for MCS110; sum of all dose administered (mg) to a patients for PDR001;
- **Cumulative planned dose:** sum of all planned dose (mg/kg) of MCS110 that were intended to have been taken during the treatment period by a patient; sum of all planned dose (mg) of PDR001 that were intended to have been taken during the treatment period by a patient;
- **Number of doses scheduled per protocol :** number of doses given to a patient if each actual cycle length is exactly 21 days and study treatment is given on day 1 of each cycle, which is calculated as: [Duration of exposure to study drug (days)/ 21 (days)] + 1*I{ Duration of exposure to study drug (days) mod 21 (days) ≠ 0}. [x] is the largest integer less than or equal to x. $b = \text{mod}(a, m)$ returns the remainder after division of a by m , where a is the dividend and m is the divisor. I{·} is a indicator function. This will be calculated for MCS110 and PDR001 separately and used for calculation of dose intensity below.
- **DI:**
 - For MCS110 (mg/kg/3wks): cumulative dose (mg/kg)/ number of doses scheduled per protocol during treatment period;
 - For PDR001 (mg/3wks): cumulative dose (mg)/ number of doses scheduled per protocol during treatment period;
- **PDI:**
 - For MCS110 (mg/kg/3wks): cumulative planned dose (mg/kg)/ number of doses scheduled per protocol during treatment period (i.e., this is equivalent to planned dose level);
 - For PDR001 (mg/3wks): planned cumulative dose (mg)/ number of doses scheduled per protocol during treatment period (i.e., this is equivalent to planned dose level);
- **RDI (%):**
 - For MCS110: $100 \times \text{DI (mg/kg/3wks)}/\text{PDI (mg/kg/3wks)}$
 - For PDR001: $100 \times \text{DI (mg/3wks)}/\text{PDI (mg/3wks)}$

Note: If a patient is still on treatment at the time of data cut-off, the end date of study treatment/drug will be replaced by the data cut-off date and the above respective algorithm will be used.

Dose interruption: Actual dose equal to zero, between the first and last non-zero doses, following a non-zero actual dose.

Dose reduction: A non-zero actual dose that is less than the immediate previous non-zero actual dose (if not the first dose) and below the treatment received dose.

Note: actual dose for MCS110 (mg/kg) = Dose prescribed (mg/kg) * Total volume administered (ml)/Total volume planned to be administered (ml); actual dose for PDR001 (mg) = Dose prescribed (mg) * Total volume administered(ml)/Total volume planned to be administered(ml).

The duration of exposure to each of the two study drugs and study treatment (including categories: ≤ 3 , $3 \leq 6$, $6 \leq 9$, $9 \leq 12$, $12 \leq 15$, $15 \leq 18$, > 18 weeks) will be summarized. In addition, the cumulative dose, DI, and RDI (including categories: < 0.5 , $0.5 < 0.75$, $0.75 < 0.9$, $0.9 < 1.1$, ≥ 1.1) will be summarized for each study drug.

To assess tolerability, the number (%) of patients who have dose reductions and interruptions, and the corresponding reasons, will be provided for each study drug. The number of dose reductions and interruptions per patient will be summarized for each study drug.

All doses of the study treatment along with reasons for any dose change will be listed.

Compliance

Compliance to study drug will be evaluated by dose reduction and dose interruption.

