6.1.1 Dosing regimen

Table 6-1 Dose and treatment schedule

Study treatments	Pharmaceutical form and route of administration	Dose	Frequency and/or Regimen
MCS110	Liquid concentrate in vial i.v. infusion	3 mg/kg (starting dose)	Every 3 weeks
PDR001	Powder for solution for infusion	100 mg (starting dose)	Every 3 weeks

MCS110 and PDR001 will be administered once every 3 weeks via i.v. infusions over 1 hour and 30 minutes, respectively. The drugs will be administered separately with at least a 30 min break between the two antibodies. Infusions of each antibody can be extended to up to 2 hours if clinically indicated.

Both study drugs may be infused using the same i.v. access site. The same administration sequence must be followed for all patients, i.e. PDR001 should be infused first. If an infusion reaction occurs after administration of PDR001, the subsequent MCS110 infusion must be delayed until it is safe for the patient to receive MCS110 based on the clinical discretion of the investigator. The delay between PDR001 and MCS110 infusions can be up to 4 hours if clinically indicated.

A scheduled dose of ongoing study drugs may be delayed by up to 7 days to recover from previous AEs or a missed visit (see [Section 6.3.2](#)). If a scheduled dose of ongoing study drugs is delayed longer than 7 days due to an unresolved AE, the administration should be skipped and treatment resumed at a lower dose level (if meeting criteria for DLT) at the next scheduled dose. The assessment schedule will be shifted accordingly. Dose delays refer to all ongoing study drugs: for combination treatment both MCS110 and PDR001 and for single agent treatment MCS110 or PDR001. Dose modifications should follow [Section 6.3.1](#) and [Section 6.3.2](#).

The dose for MCS110 study drug will be calculated from the individual subjects' body weight as measured at the screening visit and subsequent visits prior to the administration.

After Phase Ib part, if emerging PK, PD, and safety data indicate that a flat dosing strategy of MCS110 is appropriate, then a flat dosing strategy may be implemented in the Phase II part of the study. The PK data obtained during Phase Ib part of this study will be combined with PK data from the other MCS110 clinical studies to assess the flat dosing vs. body-weight based dosing, and a flat dose may be identified for the Phase II part of this study.

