10.3 Treatments (study treatment, concomitant therapies, compliance)

For each of MCS110 and PDR001, the actual dose and duration in days of treatment as well as the dose intensity (actual dose received/actual duration) and relative dose intensity (the ratio of dose intensity to planned dose/planned duration) will be listed and summarized by means of descriptive statistics by treatment group. Categories for relative dose intensity of MCS110 or PDR001 will be specified as < 0.5 , $\geq 0.5 - < 0.75$, $\geq 0.75 - < 0.9$, $\geq 0.9 - < 1.1$ and ≥ 1.1 . The number and proportion of patients within each category will be presented by treatment group.

Concomitant medications and significant non-drug therapies prior to and after the start of the study treatment will be listed by patient and summarized by ATC term and treatment group.

The reason for discontinuation from treatment will be summarized and listed, along with dates of first and last dose of MCS110 and PDR001 (if applicable), duration of exposure to MCS110 and PDR001 (if applicable) and date of discontinuation for each patient.

Compliance with the protocol will be assessed by the number and proportion of patients with protocol deviations. Protocol deviations will be identified prior to database lock and will be listed and summarized.

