2.5.1 Primary endpoint

2.5.1.1 Phase Ib part

The primary variables of Phase Ib are:

- Safety: Incidence and severity of AEs and SAEs, including changes in laboratory values, vital signs, and ECGs;
- Tolerability: Dose interruptions, reductions, and dose intensity;
- Incidence of DLTs in the first two cycles of study treatment.

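### SAP 2.4.1 rounds exposure up to whole 21-day cycles, so a fully dosed off-treatment patient with a one-day net delay gets the relative dose intensity of a patient who skipped a dose

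*SAP*

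**What the plan says.** SAP 2.4.1 builds RDI in four steps.

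- **End of exposure.** For MCS110 it is "last date of administration of MCS110 + 20 days", and PDR001 has the same rule. Duration is that date minus the first dose date plus 1, with interruptions left in.
- **Scheduled doses.** The denominator is the "number of doses given to a patient if each actual cycle length is exactly 21 days". It is the integer part of duration/21, plus 1 whenever "Duration of exposure to study drug (days) mod 21 (days") is not zero.
- **DI, PDI and RDI.** Dose intensity (DI) is cumulative dose over that count. Planned dose intensity (PDI) is cumulative planned dose over the same count, with the remark that "this is equivalent to planned dose level". RDI is 100 × DI/PDI.
- **Cut-off.** For a patient still on treatment, "the end date of study treatment/drug will be replaced by the data cut-off date".

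RDI is then reported in categories with cuts at 0.5, 0.75, 0.9 and 1.1 (SAP 2.4.1 and 2.8.4.3). SAP 2.5.1.1 lists among the Phase Ib primary variables "Tolerability: Dose interruptions, reductions, and dose intensity".

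Protocol 10.3 gives a different basis: "dose intensity (actual dose received/actual duration"), with RDI as its ratio to planned dose over planned duration. On timing, Protocol 6.1.1 says "A scheduled dose of ongoing study drugs may be delayed by up to 7 days", and Protocol 7.1 allows a visit window of ±7 days.

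**The concern.** Ending exposure at last dose + 20 days makes a perfectly timed course an exact multiple of 21 days. The rounding rule then treats one extra day like twenty-one extra days, because either adds a full scheduled dose. The error runs one way: net early dosing never takes RDI above 100%.

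The trigger is ordinary conduct that the protocol permits. Protocol 6.1.1 separates a delayed dose from a skipped one, and the SAP formula removes that distinction from DI and RDI. A patient could show no interruption and no reduction in the tolerability tables, yet an RDI of 75% beside them.

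The DI and RDI summaries and the RDI categories would understate delivered dose intensity in a component of the Phase Ib primary tolerability variable. The Amendment 05 study status reports that the 6 patients still on treatment at 08-Jul-2019 were all in Phase II. The off-treatment formula therefore governs the whole Phase Ib summary of 60 patients.

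**Working it through.** The documents state no RDI figure to reproduce, so the check applies the SAP 2.4.1 rule directly.

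**Inputs.** Cycle length 21 days; end of exposure = last dose + 20 days; scheduled doses = duration/21 rounded up; PDI = planned dose level. Let k be the number of full planned doses received. Let d be the net delay in days, that is (last dose date − first dose date) − 21(k−1).

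**Off treatment.**

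- Duration D = 21(k−1) + d + 20 + 1 = 21k + d.
- On time (d = 0): D/21 = k, so RDI = k/k = 100%. The rule works here.
- Delay of 1 to 21 days: D/21 rounds up to k+1, so RDI = k/(k+1).
- One dose truly skipped, otherwise on time: D = 21(k+1), so there are k+1 scheduled doses and RDI = k/(k+1). This is the same value.
- Without rounding: RDI = k/(D/21) = 21k/(21k + d).

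| k | SAP RDI, d = 1–21 | SAP category | Unrounded, d = 1 | Unrounded, d = 7 |
|---|---|---|---|---|
| 2 | 2/3 = 66.7% | 0.5–<0.75 | 42/43 = 97.7% | 42/49 = 85.7% |
| 3 | 3/4 = 75.0% | 0.75–<0.9 | 63/64 = 98.4% | 63/70 = 90.0% |
| 4 | 4/5 = 80.0% | 0.75–<0.9 | 84/85 = 98.8% | 84/91 = 92.3% |
| 5 | 5/6 = 83.3% | 0.75–<0.9 | 105/106 = 99.1% | 105/112 = 93.8% |
| 6 | 6/7 = 85.7% | 0.75–<0.9 | 126/127 = 99.2% | 126/133 = 94.7% |
| 7 | 7/8 = 87.5% | 0.75–<0.9 | 147/148 = 99.3% | 147/154 = 95.5% |
| 8 | 8/9 = 88.9% | 0.75–<0.9 | 168/169 = 99.4% | 168/175 = 96.0% |
| 9 | 9/10 = 90.0% | 0.9–<1.1 | 189/190 = 99.5% | 189/196 = 96.4% |

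One-dose patients cannot have a delay and score 100%. For k of 9 or more and d up to 21, RDI stays at or above 0.9.

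**Category shifts.** Over k = 2–8 and d = 1–7 there are 7 × 7 = 49 combinations, and the SAP rule puts all of them below 0.9. Unrounded RDI is below 0.9 in only three: k=2 with d=5, 6 or 7 (42/47 = 89.4%, 42/48 = 87.5%, 42/49 = 85.7%). Rounding alone therefore moves 46 of the 49. These are grid cells, not a forecast of patient numbers.

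**Early dosing.** For k=4 and d=−3, D = 81. The SAP count is 4 and RDI is 100%; unrounded it is 84/81 = 103.7%.

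**Still on treatment, on schedule, cut-off on day j of cycle k.** The cut-off note has two readings.

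- Cut-off replaces the end of exposure: D = 21(k−1) + j, which rounds up to k cycles, so RDI = 100%.
- Cut-off replaces the last administration and 20 days are added: D = 21k + (j−1). For j = 2 to 21 this rounds up to k+1, so RDI = k/(k+1), for example 6/7 = 85.7% at k=6.

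Dropping the rounding while ending D at cut-off would overshoot: at k=9, day 1, D = 169 and RDI = 189/169 = 112%. The cut-off rule has to be settled together with the rounding.

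**The case against.** The strongest defence is that the formula counts what it says it counts. A window of 21k+1 days does contain k+1 day-1 dosing dates, so this is a coarse convention rather than a slip of calculation. Protocol 10.3 also leaves actual and planned duration undefined. Both points are fair, but charging one extra day as a whole dose is not dose over duration in any usual sense. SAP section 4 also lists only the change from +21 to +20 days for 2.4.1, not a departure from the protocol's definition.

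A second defence reads cumulative planned dose as covering only the k doses given. The count then cancels and RDI is 100%. But PDI would be k/(k+1) of the planned dose level, against the SAP's own remark, and DI would still be understated.

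Third, missed doses are reported through interruption counts, compliance is judged on interruptions and reductions, and every dose is listed. That stands: the SAP would not record a missed dose. It would give an RDI equal to that after one.

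Fourth, the primary report waits until patients have completed six cycles or discontinued, so the cut-off ambiguity should concern patients with about six or more doses, and on the reported status only Phase II. That limits the cut-off point and leaves the off-treatment result intact.

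Finally, unrounded RDI can exceed 1.1 when doses come early: two doses 7 days early give 42/35 = 120%. That is a true rise in dose per unit time, and the reporting category of 1.1 and above exists for it.

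**Conclusion.** The concern holds, and the rule should be fixed. As written, SAP 2.4.1 gives every fully dosed off-treatment patient with a net delay of 1 to 21 days an RDI of k/(k+1). That moves patients with 2 to 8 doses below 0.9 even when the delay is one day and the proportionate value is 97.7% or higher. The result assumes all k doses were at the full planned level and that PDI equals the planned dose level, as the SAP says.

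The documents give no distribution of doses or delays, so the number of patients affected is unknown. The outputs are descriptive. ORR, CBR, the DLT model, and the interruption and reduction counts do not change. The unclear cut-off note is a smaller, related point.

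**What to change.** In SAP 2.4.1:

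- Define DI = cumulative dose / (D/21), without rounding.
- Define PDI simply as the planned dose level, and RDI = 100 × DI / planned dose level. The scheduled-dose bullet then has no further use in these formulas.
- For patients still on treatment, end D for this calculation at the later of last administration + 20 days and the cut-off date, and reword the cut-off note to say so. An on-schedule patient on day j of cycle k then has D = max(21k, 21(k−1)+j) = 21k and scores 100% on any cut-off day, while an overdue dose still lowers RDI.
- State that this D serves dose intensity only, since it can run past the cut-off date.

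The cost is a few lines of SAP text and the matching dataset specification. No new data are needed and no dosing rule changes.

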10.4.1 Variable

Phase Ib

The primary variables of Phase Ib are:

- Safety: Incidence and severity of AEs and SAEs, including changes in laboratory values, vital signs, and ECGs;
- Tolerability: Dose interruptions, reductions, and dose intensity;
- Incidence of DLTs in the first two cycles of study treatment

Phase II

For TNBC, endometrial carcinoma and melanoma the primary variable of Phase II is the Overall Response Rate (ORR), defined as the proportion of patients with a best overall response of complete response (CR) or partial response (PR) based on local Investigator assessment, as defined in RECIST v1.1. Estimation of the true ORR in this part of the study will be based upon the observed BOR for patients in the FAS, using a Bayesian analysis.

For pancreatic patients, the primary variable of Phase II is the Clinical Benefit Rate (CBR), defined as the proportion of patients with a best overall response of complete response (CR) or partial response (PR) (with at least two assessments 4 weeks apart) or stable disease (SD) > 4 months based on local Investigator assessment, as defined in RECIST v1.1.

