2.2.2 Safety Set

The safety set (SS) includes all patients who have received at least one dose of MCS110 or PDR001. Patients will be classified according to treatment received, where treatment received is defined as:

1. The treatment assigned if it was received at least once, or
2. The first treatment received when starting therapy with study treatment if the assigned treatment was never received.

The safety set will be used for the safety summary of the study.

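### SAP 2.4.1 derives dose reductions from infused volume with no tolerance, so an incomplete infusion can be counted as a reduction when no lower dose level was prescribed

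*SAP*

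**What the plan says.** SAP 2.4.1 sets two conditions for a dose reduction. The first is "A non-zero actual dose that is less than the immediate previous non-zero actual dose". The text then continues: "if not the first dose) and below the treatment received dose". A note gives the formula: "actual dose for MCS110 (mg/kg) = Dose prescribed (mg/kg) * Total volume administered (ml)/Total volume planned to be administered (ml". The PDR001 formula is the same, in mg. No minimum difference or tolerance is stated.

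The same section defines a prescribed dose, "Prescribed dose is the dose level(s) of study drug(s) prescribed by doctor before study treatment is administered at beginning of each cycle", but does not use it as the comparator. Treatment received comes from SAP 2.2.2: "The treatment assigned if it was received at least once".

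The results feed "the number (%) of patients who have dose reductions and interruptions, and the corresponding reasons", a count of reductions per patient for each drug, and the evaluation of compliance. SAP 2.8.4.3 reports them by treatment group in Phase Ib. Protocol 10.4.1 lists them as a Phase Ib primary variable: "Tolerability: Dose interruptions, reductions, and dose intensity".

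The protocol itself uses the term for a step to a lower dose level (footnote to Table 6-2; Section 6.3.1).

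**The concern.** Two different events share one label. One is a decision to prescribe a lower dose level because the patient did not tolerate the current one. The other is a bag that was not fully infused, or a volume recorded slightly below plan. The first is what the protocol means by a reduction and what a reader of a tolerability table expects. Under the SAP rule the second qualifies as well, however small the shortfall.

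The comparator is also volume-adjusted. What is flagged after an incomplete infusion therefore depends on how much of that infusion was delivered, and not only on whether the prescribed level changed.

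At stake is a descriptive but primary output in small groups, read by dose and by reason.

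**Working it through.** The documents state no figure on this point, so the rule was applied literally to short dose sequences.

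**Inputs.** The rule and formula are from SAP 2.4.1. Dose levels are from Protocol Table 6-2, plus the 7.5 mg/kg level used in the study. Infused shares are illustrative assumptions. Group sizes are from the Amendment 04 study status: 6, 12, 12, 13, 6 and 11 patients, 60 in total.

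**Rule as coded.** Actual = prescribed × volume given / volume planned. Flag if actual < previous non-zero actual and actual < treatment received dose.

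| Prescribed (share infused if not 100%) | Actual dose | SAP flags | Prescribed level falls |
|---|---|---|---|
| MCS110 7.5, 5 | 7.5, 5 | dose 2 | dose 2 |
| MCS110 7.5, 7.5 (99%), 7.5 | 7.5, 7.425, 7.5 | dose 2 | never |
| MCS110 7.5, 7.5 (50%), 7.5 | 7.5, 3.75, 7.5 | dose 2 | never |
| MCS110 7.5, 7.5 (90%), 5, 5 | 7.5, 6.75, 5, 5 | doses 2 and 3 | dose 3 |
| MCS110 7.5, 7.5 (50%), 5, 5 | 7.5, 3.75, 5, 5 | dose 2 | dose 3 |
| PDR001 300, 300 (50%), 100 | 300, 150, 100 | doses 2 and 3 | dose 3 |
| PDR001 300, 300 (30%), 100 | 300, 90, 100 | dose 2 | dose 3 |
| MCS110 7.5 (50%), 5, 5 | 3.75, 5, 5 | none, or dose 1 | dose 2 |

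The first row is a check: with complete infusions the rule works. The last row has two results because the parenthesis on the first dose can be read two ways. Either a first dose can never qualify, or only the comparison with a previous dose is waived.

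**Overcount.** The second condition does not help, because any incomplete infusion of the assigned dose is below the treatment received dose. Two protocol rules show the gap:
- Section 6.3.1 permits no reduction below PDR001 100 mg. In the 18 patients treated at 100 mg (6 + 12), a PDR001 reduction counted by the SAP would reflect volume alone, unless there was a deviation or an individually agreed dose.
- Section 6.3.1 allows dose modification in the first two cycles only after a DLT. A 98% infusion in Cycle 2 after a full Cycle 1 dose would still be tabulated as a reduction.

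**Missed level reduction.** Let f be the share infused at the old level, with the next dose fully infused at the new level. The fall is not flagged when f × old ≤ new, that is, f ≤ new/old:
- 10 to 7.5 mg/kg: 75%
- 7.5 to 5: 66.7%
- 5 to 3: 60%
- 10 to 5: 50%
- 3 to 1: 33.3%
- 1 to 0.3: 30%
- PDR001 300 to 100 mg: 33.3%

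Above the threshold the level reduction is flagged and the incomplete infusion is counted as well.

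**Size of the overcount.** Let q be the share of infusions recorded below planned volume. It is not in the documents, so 1% to 5% is assumed. With independent infusions, each shortfall following a fuller infusion, and the first dose excluded, the chance of at least one false reduction in k doses of one drug is 1 − (1 − q)^(k−1).

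| | q = 1% | q = 2% | q = 5% |
|---|---|---|---|
| One patient, 6 doses | 4.9% | 9.6% | 22.6% |
| One patient, 10 doses | 8.6% | 16.6% | 37.0% |
| At least one of 6 patients, 6 doses each (30 later infusions, 1 − (1 − q)^30) | 26% | 45% | 79% |

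One falsely counted patient adds 1/6 = 16.7 percentage points in a group of 6 and 1/13 = 7.7 in a group of 13.

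**The case against.** An actual-dose definition is a legitimate exposure measure, and the SAP offers several safeguards. All doses are listed with reasons for any change. Reasons are tabulated with the counts. The relative dose intensity band from 0.9 to below 1.1 absorbs a 1% or 2% shortfall. Tolerability is descriptive, and the dose-escalation model uses DLTs rather than reductions. Derivation details sit in a separate programming specification that is not available here and might contain a tolerance. All of this limits the consequence. None of it changes the rule as written or corrects the summary counts.

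A reader might go further and infer that a true level reduction after an incomplete infusion is generally lost, so that comparison between doses is wrong in both directions. The documents do not support that:
- The loss occurs only at or below the thresholds shown above.
- Where the incomplete infusion followed a fuller dose, the patient and one event are still counted. Only the date, and possibly the reason, is wrong.
- The patient disappears only if the incomplete infusion was the first dose and the parenthesis bars that dose from qualifying.
- The sequence is not the routine path. The infusion-reaction rows of Protocol Table 6-4 slow, interrupt or stop treatment and do not call for a lower level. The rows that explicitly lower MCS110 concern CK elevation and periorbital edema.

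**Conclusion.** The overcount is a direct result of the stated rule. An incomplete infusion of the assigned dose that follows a fuller one is a dose reduction, whatever the shortfall and whether or not a lower level was prescribed. It can inflate both the number of patients with reductions and the counts per patient. Its actual size cannot be established from the documents, because it rests on an under-volume rate they do not give; the percentages above show a range under assumed rates.

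The missed level reduction is a secondary and conditional effect, and mostly one of misdating or a wrong reason. The handling of the first dose is ambiguous and needs stating in any case. The SAP should be changed, since this is a primary tolerability variable in small groups and the correction is cheap.

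**What to change.** In SAP 2.4.1:
- Define a dose reduction as a prescribed dose level of that drug lower than its previous prescribed level and below the treatment received dose level. Keeping the second condition matters: without it, a return to the assigned dose after intra-patient escalation (Protocol 6.2.3.2) would newly count as a reduction.
- Report incomplete infusions, with administered volume below planned by a margin that the sponsor sets, as a separate category with their reasons.
- State how the first dose is handled.
- Keep volume-adjusted actual dose for cumulative dose, dose intensity and relative dose intensity.

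Applied to the sequences above, this gives no reduction for the 99% and 50% infusions without a level change, and exactly one, at the right dose, in every sequence where the level falls.

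The cost is a small programming change, one extra summary row and an SAP amendment (an addendum if the database is already locked). Prescribed dose and both volumes are already inputs to the SAP formula. The programming specification should be checked for consistency. No dosing rule is affected.
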